9.3.2 Evaluable Population

The Evaluable Population is defined as all patients who undergo PAE with Embosphere Microspheres, have valid IPSS data for the 12 month time point, and do not have any major protocol violations.

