3.2 Exclusion Criteria

Patients that meet any of the following exclusion criteria will not be eligible for this study.

1. History of prostate, bladder or rectal malignancy. Biopsy proven urethral cancer.
2. History of rectal disease
3. Neurogenic bladder disorder due to multiple sclerosis, Parkinson's disease, spinal cord injury, diabetes, etc., as demonstrated on urodynamic testing.
4. Detrusor muscle failure, urethral stenosis, or urinary obstruction due to causes other than BPH, as demonstrated on urodynamic testing
5. Bladder diverticula greater than 5 cm or bladder stones greater than 2 cm
6. Cystolithiasis within the past three months
7. Baseline serum creatinine greater than 1.8
8. Evidence of tortuous or atherosclerotic blood vessels
9. Presence of collateral vessel pathways potentially endangering normal territories during embolization that cannot be bypassed with the microcatheter
10. Active urinary tract infection, interstitial cystitis, or prostatitis within the last 5 years
11. Coagulation disturbances not normalized by medical treatment
12. Allergy to iodinated contrast agents not responsive to steroid premedication regimen
13. Previous radical pelvic or rectal surgery, or pelvic irradiation
14. Prior surgical prostate intervention
15. Treatment with beta-blocker, antihistamine, anticonvulsant, or antispasmodic medication within 1 week of treatment UNLESS there has been a stable voiding pattern while medicated with the drug(s) for 6 months
16. Use of prostate active medications, including alpha blockers, anti-cholinergics, androgens, anti-androgens, gonadotropins-releasing hormonal analogs, PDE5-inhibitors, 5-alpha reductase inhibitors within 2 months of intervention, unless the medication is necessary to avoid symptom exacerbation and disability, in this case medication should not be initiated or dose adjusted within 1 month of study enrollment and dose should not be adjusted during the study period
17. Interest in future fertility
18. Mental condition or disorder that interferes with participants' ability to provide written informed consent

19. Current severe or uncontrolled disease (metabolic, hematologic, renal, hepatic, pulmonary, neurologic, cardiac, infectious or gastrointestinal) that in the Investigator's judgment makes the patient unsuitable for trial inclusion due to increased risk of complications
20. Known immunosuppression
21. Life expectancy less than 6 months

4. Study Design

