9.2 Sample Size Calculations

This is a phase I/II, single center, prospective, single arm, investigational study to evaluate the safety and efficacy of prostate artery embolization (PAE) for treatment of severe LUTS related to BPH in patients with prostate size between 40 and 300 cm³ that have either failed or are intolerant to medical management. Twenty patients treated with PAE with Embosphere Microspheres are considered sufficient to provide data that will be used to evaluate the study objectives. No formal sample size calculations have been performed.

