9.3 Analysis Populations

9.3.1 Intent-to-Treat Population

The Intent-to-Treat (ITT) Population is defined as all patients who undergo PAE with Embosphere Microspheres. This will be the primary population for all efficacy analyses.

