9.5 Efficacy Analyses

All efficacy analyses will be based on the ITT Population on the locked database after all patients have completed the 12 month follow-up visit or are lost to follow-up. If <15% of patients are excluded from the Evaluable Population, only the analyses of the ITT Population will be presented in the summary tables. If >15% of patients are excluded from the Evaluable Population, secondary efficacy analyses of the primary efficacy outcome will be performed on the Evaluable Population and included in the summary tables.

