9.5.1 International Prostate Symptom Score (IPSS)

The primary efficacy outcome will be based on the IPSS. The IPSS is a frequent used, validated, 8 item (7 symptom burden questions and 1 quality of life question) instrument which can be serially performed to compare the progression of symptoms and their severity over months and years. Patients are asked to assess how often they have experienced the following 7 symptoms in the past month: incomplete emptying, frequency, intermittency, urgency, weak urine stream, straining and nocturia. The response categories range from 0=Not at all to 5=Almost always. The total IPSS score is calculated by summing the responses for the 7 symptom burden items. The eighth item is an assessment of patient quality of life due to LUTS and does not contribute to the IPSS score calculation.

Patients will be classified into one of 3 symptom severity categories based on their total IPSS score as follows:

- Mildly symptomatic: 0-7
- Moderately symptomatic: 8-19
- Severely symptomatic: 20-35

The IPSS total score will be summarized for the baseline, 1 month, 6 month and 12 month time points, including change from baseline. Change from baseline will be calculated as post baseline IPSS score minus baseline IPSS score. A negative value indicates symptom improvement. 95% confidence intervals will be calculated for the mean change from baseline to the post baseline time points. For informational purposes, IPSS scores will also be summarized separately for patients that receive unilateral and bilateral PAE if there are sufficient numbers in both groups.

The primary efficacy analysis will be the change in IPSS total score from baseline to 12 months post PAE for the ITT population. A Paired-Sample Wilcoxon Signed Rank Test will be used to assess the statistical significance of the change from baseline to 12 months post PAE. A secondary analysis of the proportion of patients who have improved by at least one IPSS symptom category (i.e., severe to moderate, severe to mild, or moderate to mild) from baseline to 12 months post PAE will also be performed. A 95% confidence interval will be calculated for the proportion. The proportion of patients improving at least 3 points on the IPSS total score at the 12 month time point will also be summarized and the corresponding 95% confidence interval will be calculated.

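### Drug changes after PAE can decide who is in the Evaluable Population, and the responder proportions credit PAE with improvement that follows added BPH treatment

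*Combined protocol and SAP*

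**What the plan says.** Exclusion item 16 (Section 3.2) keeps out men who used prostate-active drugs within 2 months of the intervention, "unless the medication is necessary to avoid symptom exacerbation and disability". For men admitted under that exception, it adds that the "dose should not be adjusted during the study period". A condition on conduct after treatment thus sits inside an eligibility criterion.

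Section 9.3.2 restricts the Evaluable Population to treated men who "have valid IPSS data for the 12 month time point, and do not have any major protocol violations". The document does not define a major violation, name who decides, or give a date by which the decision is made. Appendix A has protocol violations and concomitant medications recorded from screening to Month 12.

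Section 9.3.1 says of the ITT Population, which is all treated men: "This will be the primary population for all efficacy analyses". Section 9.5.1 agrees: "The primary efficacy analysis will be the change in IPSS total score from baseline to 12 months post PAE for the ITT population". Section 9.5 makes the Evaluable analysis conditional: "If >15% of patients are excluded from the Evaluable Population, secondary efficacy analyses of the primary efficacy outcome will be performed".

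Section 9.5.1 also plans two responder proportions at 12 months, one for a better severity category and one for a gain of 3 points or more. Both use the IPSS total alone. Section 9.5.7 uses all available data, with LOCF for gaps. No rule covers scores recorded after a drug increase or a new BPH treatment.

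**The concern.** There are two separate gaps.

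The first is membership of the Evaluable Population. A man whose symptoms persist after PAE and whose continued drug is increased has broken item 16. If that is judged major, he leaves the Evaluable Population although his 12-month IPSS exists. A man who improves and cuts his dose can leave by the same route. In a single-arm study, whoever makes the judgement can already know how he did. An analysis set whose membership depends on the outcome is not a sound check on the ITT result.

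The second gap applies to ITT as well. A man who fails PAE, has his drug increased or receives another BPH treatment, and then improves counts as a PAE success. With no control arm, readers will take the proportion as the effect of PAE.

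**Working it through.** The plan has no figure to reproduce; Section 9.2 says "No formal sample size calculations have been performed". The document gives no rate of drug increase, no share of men continuing drugs and no SD. The sizes below are illustrations.

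**Inputs.** 20 treated men (Section 9.2). The 15% trigger (Section 9.5). One-year clinical success of 75.2% in the 255-patient series cited in the background, so a failure rate of 1 − 0.752 = 24.8%, about 5 of 20. A 6.7-point improvement in the background's 15-patient series, assumed to be on an IPSS-like scale; 10 points is tried as well. Failures are assumed to change by 0 on PAE alone.

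**1. Trigger.** With the ITT Population as denominator, 3/20 = 15.0% and 4/20 = 20.0%. So 4 exclusions are needed, for any reason, including a missing 12-month IPSS. Neither sentence of the rule covers exactly 15%. If only 19 men are treated, 3/19 = 15.8% is enough.

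**2. Chance that drug-increased failures alone reach 4.** P(X ≥ 4), X ~ Binomial(20, f × s), where f is the failure rate and s the share of failures removed this way:

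| f (background source) | s = 0.25 | 0.50 | 0.75 | 1.00 |
|---|---|---|---|---|
| 24.8% (1 year, 255-patient series) | 3% | 23% | 53% | 77% |
| 18.1% (1 month, same series) | 1% | 10% | 28% | 50% |
| 9.4% (PAE arm, trial against TURP) | 0.1% | 1% | 5% | 11% |

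**3. Effect on the Evaluable result if 4 of 5 failures are removed.**
- Responders: 15/20 = 75% (95% CI 51–91%) becomes 15/16 = 94% (70–100%).
- Mean change, responders −6.7: 15 × (−6.7)/20 = −5.03 becomes 15 × (−6.7)/16 = −6.28, a shift of 1.26.
- Mean change, responders −10: −150/20 = −7.50 becomes −150/16 = −9.38, a shift of 1.88.
- With 6 failures instead of 5, and responders at −10: 14/20 = 70% becomes 14/16 = 88%, and the mean goes from −7.0 to −8.75.

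**4. Opposite direction.** If 4 improvers who lowered their dose are removed instead (5 failures, responders −10): 11/16 = 69% against 75%, and −110/16 = −6.88 against −7.50.

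**5. Effect of added treatment on ITT.** Suppose 4 of the 5 failures have their drug increased and each score falls by 5.
- The ITT mean moves by 4 × (−5)/20 = −1.0, from −5.03 to −6.03 or from −7.50 to −8.50.
- All 4 meet the 3-point criterion, so the proportion is 19/20 = 95% instead of 15/20 = 75%. Each such man adds 1/20 = 5 percentage points.
- For the category proportion, a man starting at 20 to 24 who falls by 5 lands at 15 to 19 and moves from severe to moderate.

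The Evaluable mean in step 3 then exceeds this ITT mean by 0.26 or 0.88. If the drug increase has no effect, it exceeds the ITT mean by 1.26 or 1.88.

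**The case against.** Much of the case on the other side stands.
- A reader might infer that Section 9.3.2 requires these men to be removed. It does not. It removes only major violators, and nothing in the document classes a dose change as major.
- The dose rule covers only men continued on a drug under the exception. Inclusion item 5 requires men to be refractory to or intolerant of medical management, so drug increases may be uncommon. Nothing supports 4 increases among 5 failures as an expected number.
- A reader might infer that the primary result is biased by this exclusion. It is not, because ITT keeps every treated man and remains the main report.
- A reader might take the Evaluable analysis as the plan's main check on ITT. Section 9.5.7 also plans multiple imputation if data are missing at random, although that addresses missing scores, not removed men.
- One to three removals alone do not trigger the analysis with 20 treated. Section 9.5 runs only the primary efficacy outcome on the Evaluable set, so it is unclear whether the responder proportions would be produced there.
- Medications are listed by patient and violations are recorded, so removals could be traced.

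Counting added treatment as non-response is also one choice among several. It is the choice that fits an objective of improvement after PAE in a study without a comparator. None of these points touches the crediting gap in Section 9.5.1.

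**Conclusion.** The point holds in limited form. Item 16 and Section 9.3.2 together allow membership of the Evaluable Population to depend on outcome. They do not prescribe it, and the documents do not support the stronger claim that the Evaluable result will overstate benefit: removing failures pushes it up, while removing improvers who cut their dose pulls it down. The consequence is confined to a secondary analysis that appears only with at least 4 of 20 excluded.

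The responder rule matters more, because it acts in the ITT Population whatever the exclusions. Each man who improves by 3 points or more only after added treatment raises the 3-point proportion by 5 percentage points. Under the same assumptions the ITT mean is inflated by 0 to 1.0 point, for a drug effect of 0 to 5 points in 4 men. The contrasts of 75% with 94% and 70% with 88% show what is possible on assumed numbers; they are not forecasts.

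**What to change.** Before database lock:

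1. In Section 9.5.1, count a man with a post-PAE increase in BPH/LUTS medication, or a new BPH/LUTS treatment, before month 12 as a non-responder in both the 3-point and the category proportions. Apply this to ITT, and to the Evaluable Population if it is run. Add a sensitivity analysis of mean IPSS change that treats such men as unchanged from baseline.
2. In Section 9.3.2, state that post-PAE changes in BPH/LUTS medication or treatment are not by themselves grounds for removal, and identify these men in the summary table.

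Item 16 and Section 9.3.2 should be reconciled for analysis purposes only. No dose rule changes.

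The cost is a few sentences and responder figures that become slightly less favourable. Medication data are already collected to Month 12. Sections 5.3 and 5.4 ask expressly about new BPH/LUTS treatments only when a man does not return, so it should be confirmed that the same information is recorded for men who attend.

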9.3.3 Safety Population

The Safety Population is defined as all patients who undergo PAE with Embosphere Microspheres. This is the same as the ITT Population.

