7.2 Adverse Event Reporting

The Investigators are responsible for monitoring the safety of patients who have been enrolled in this study. All AEs considered to be related to study treatment will be followed until the event resolves or has reached a fatal outcome. Adverse events will be evaluated for severity and graded following the Common Terminology Criteria for Adverse Events (CTCAE) version 4.0 as follows: Grade 1 (mild)- asymptomatic or mild symptoms; intervention not indicated, Grade 2 (moderate)- minimal symptoms; local or noninvasive intervention indicated, Grade 3 (severe)- medically significant but not immediately life threatening; hospitalization or prolonged hospitalization indicated, Grade 4 (life-threatening)- urgent intervention indicated, Grade 5- death related to AE.

The principle investigator will determine with attribution of each AE. AEs will be categorized into one of five classes: definite- clearly related to ____, probable- likely related to ____, possible- may be related to ____, unlikely- doubtfully related to ____, or unrelated- clearly not related to ____.

Attempts will be made to identify what the AE is related to and not merely what it is not related to.

The Investigators will document all AEs occurring during the study, commencing with the date of PAE treatment and including the protocol-defined post treatment follow-up period (21 CRF §312.64[b]), which is defined as 12 months post date of PAE, on the AE CRF. AEs and SAEs that occur following the signature of informed consent but prior to treatment will not be captured or reported.

The protocol will be terminated following the first occurrence of a serious adverse event, specifically nontarget pelvic embolization or procedure-related death.

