9.6 Safety Analyses

All safety analyses will be based on the Safety Population on the locked database after all patients have completed the 12 month follow-up visit or are lost to follow-up.

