9.6.1 Adverse Events

Safety summaries will include the incidence of treatment-emergent adverse events (TEAEs). TEAEs are defined as any adverse event (AE) that began on or after the date of treatment or worsened in severity or frequency after treatment was initiated. Events worsening in severity should be considered new AEs.

All TEAEs will be coded using the Medical Dictionary for Regulatory Activities (MedDRA) and summaries will present data by System Organ Class (SOC) and Preferred Term. TEAEs will be graded for severity into 1 of 5 classes following CTCAE version 4.0 criteria.

TEAEs will be summarized both based on the number of patients experiencing an event and as a summary of total number of TEAEs experienced by MedDRA, SOC, and Preferred Term.

A summary table will be created summarizing the number and percentage of patients with the following:

- At least one TEAE
- At least one severe TEAE
- At least one TEAE related to the study procedure or study device
- At least one treatment-emergent SAE
- At least one treatment-emergent SAE related to the study procedure or study device
- At least one TEAE leading to discontinuation of study participation
- At least one TEAE resulting in death

Separate summaries will be generated for the following types of TEAEs:

- Overall TEAEs
- Severe TEAEs
- TEAEs related to the study procedure or study device
- SAEs
- SAEs related to the study procedure or study device
- TEAEs resulting in death

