Appendix C: Technical Protocol for Prostate Artery Embolization

- Administer prophylactic IV antibiotics, based on institution standard of care. Choice of antibiotic and sedation will be at the discretion of the interventional radiologist.
- Prior to embolization, insert a Foley catheter into patient's bladder and fill it with a mixture of 50% contrast agent and 50% saline. This will provide a visual landmark during angiography.
- Local anesthesia should be administered for a transfemoral approach on the side with the best arterial pulse.
- Conduct pelvic angiography with a 5Fr catheter to evaluate aortoiliac vessels and prostate arteries during the arterial and late phases.
- Observe closely for vascular conditions and blood flow that might preclude catheter placement or embolic injection, including severe atheromatous disease, arteriovenous shunt, or presence of feeding arteries that are too small to accept the microspheres. If these conditions are present and a viable feeding artery without these problems cannot be identified, embolization will be conducted on the contralateral side of the prostate. If these conditions are present on both sides of the prostate, no embolization will be performed.
- If appropriate, anastomoses to non-targeted vessels and/or endangering collateral vessel pathways will be closed off with a larger size of embolic particles or embolic coils chosen to be appropriate to the size of the anastomosis or collateral vessel. If anastomoses or endangering collateral vessels cannot be closed off, the embolization will be performed only on the contralateral side of the prostate, if it is not affected by the condition. If anastomosis or endangering collateral vessels affects both sides of the prostate, no embolization will be performed.
- If vasospasm occurs, follow institution standard of care, which could include withdrawing the catheter slightly and waiting, or delivering a small amount of nitroglycerin. If the vasospasm cannot be resolved, conduct the embolization only on the contralateral side of the prostate.
- Ensure that the tip of the micro catheter is at or inside the ostium of the prostate arteries with additional angiography.
- Procedural endpoint is stasis of the terminal branches of the arteries feeding the prostate, while maintaining patency of the main artery branches.

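### Read literally, the Safety Population omits men whose procedure is started but who receive no microspheres, so their procedural harms may be missing from the safety tables

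*Combined protocol and SAP*

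**What the plan says.** Section 9.3.3 defines the safety set: "The Safety Population is defined as all patients who undergo PAE with Embosphere Microspheres. This is the same as the ITT Population". Section 9.6 then says "All safety analyses will be based on the Safety Population on the locked database", so no safety table rests on any other set.

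Appendix C describes the procedure in order. The bladder catheter and the femoral approach come first, and then the operator is told: "Conduct pelvic angiography with a 5Fr catheter to evaluate aortoiliac vessels and prostate arteries". What is seen there can end the procedure. For unsuitable vessels or flow: "If these conditions are present on both sides of the prostate, no embolization will be performed". For dangerous connections to other vessels that cannot be closed off: "If anastomosis or endangering collateral vessels affects both sides of the prostate, no embolization will be performed".

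Section 9.6.1 includes a table row for "At least one TEAE related to the study procedure or study device" and dates events by treatment: "TEAEs are defined as any adverse event (AE) that began on or after the date of treatment". Section 7.2 starts adverse-event documentation in the same way, "commencing with the date of PAE treatment and including the protocol-defined post treatment follow-up period", with a follow-up of 12 months from the date of PAE, and says that events between consent and treatment are not captured. Section 4 promises follow-up to treated participants. Section 9.1 puts all CRF data in the listings but removes screen failures from tables, listings and analyses.

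**The concern.** The plan itself foresees men who are exposed to the procedure but not to the device, and it assigns them to no population. Applied as written, 9.3.3 leaves them out of both the numerator and the denominator of every safety table.

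The harms at stake do not need microspheres. Section 7.1 lists pseudoaneurysm, inguinal hematoma, vascular perforation, sedation risks and contrast allergy, all of which can follow access and angiography alone. Section 4 names safety as a purpose of the study, and 2.2 puts PAE-related and overall adverse events first among the secondary objectives. In a 20-patient study, one omitted event changes what the table says.

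Two further gaps follow. Exclusion 9 concerns collateral vessels that the microcatheter cannot get past, which may become clear only at catheterisation. Such a man could then be called a screen failure and lost from the listings too. It is also unstated whether an abandoned procedure has a treatment date, and so whether his later adverse events are collected.

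**Working it through.** **Step 1: follow one man through the text.** He consents, passes screening, has the catheter, femoral access and angiography on Day 1, and meets one of the two Appendix C stopping conditions on both sides.

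- Safety Population (9.3.3): he received no Embosphere Microspheres, so on the literal reading he is out. The ITT set (9.3.1) has the same definition, and the Evaluable set (9.3.2) requires the same treatment.
- Tables (9.6): based on the Safety Population, so he is out.
- Listings (9.1): in, unless he is classed as a screen failure. Section 9.5.7, on missing efficacy data, speaks only of treated patients.
- Same-day events: probably recorded. Section 5.2 collects procedure adverse events, Appendix A ticks adverse events on Day 1, and 7.2 and 9.6.1 work by date.
- Later events: not settled, because 4 and 7.2 tie follow-up to treated men and to the date of PAE.

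A man embolised on one side only does receive microspheres and is not affected.

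**Step 2: chance that an injury is omitted.** The plan states no figure to reproduce; 9.2 says that no sample size calculation was done. Inputs, all assumptions:

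- Procedures started: n = 20. Section 4 counts 20 enrolled from consent, and 9.2 refers to 20 treated.
- Abandonment rate p: 2%, 5%, 10%. The nearest figure is 90% technical success in one earlier trial (background, Section 1). It is undefined there, so 10% is only an upper anchor.
- Injury rate q, independent of abandonment: 2%, 5%, 10%.

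Formula: P(at least one abandoned and injured) = 1 − (1 − pq)^20. For example, p = q = 0.02 gives 1 − (0.9996)^20 = 0.0080, and p = q = 0.10 gives 1 − (0.99)^20 = 0.1821.

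| p | q = 2% | q = 5% | q = 10% |
|---|---|---|---|
| 2% | 0.8% | 2.0% | 3.9% |
| 5% | 2.0% | 4.9% | 9.5% |
| 10% | 3.9% | 9.5% | 18.2% |

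The expected number of abandoned cases, 20p, is 0.4, 1 and 2.

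**Step 3: effect on a table if it happens.** Suppose 2 of 20 are abandoned and one of them has the only injury. Exact (Clopper-Pearson) 95% intervals:

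- As planned: 0/18 = 0% (0% to 18.5%)
- All started procedures counted: 1/20 = 5% (0.1% to 24.9%)

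If instead 20 men are embolised and 2 more are abandoned, the contrast is 0/20 (0% to 16.8%) against 1/22 = 4.5% (0.1% to 22.8%).

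**The case against.** The strongest reply is that undergoing PAE can include an attempt. Section 5.2 says that PAE is performed according to Appendix C, and Appendix C contains the stopping branches. Section 7.1 lists hematoma, perforation and contrast allergy among the harms of PAE itself. This reading is available, so a reader should not conclude that these men are certainly excluded. But the reference to Embosphere Microspheres in 9.3.3 strains it, and two defensible readings with different denominators need to be resolved.

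Second, these cases should be uncommon. Section 5.1 requires pelvic CT angiography before the procedure, and exclusions 8 and 9 target much of the same anatomy. That stands, although Appendix C still provides for what screening misses.

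Third, serious harms have other routes: 7.3 sends serious and unanticipated events to the FDA within 3 days, and under 7.2 a procedure-related death ends the protocol. A reader might infer that harms in abandoned cases go unrecorded; the documents do not support that. These routes do not, however, put the man in a summary table, and 7.3 does not cover an anticipated, non-serious event.

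Two other inferences go too far. The row in 9.6.1 for events related to procedure or device is an attribution category that works among embolised men, so it does not contradict 9.3.3. And the chance of at least one abandoned case, 1 − (1 − p)^20 = 33%, 64% or 88% at 2%, 5% or 10%, does not measure the problem, because an abandoned case is not in itself a harm. Nor can 10% be read as an abandonment rate: the technical-success figure behind it may count unilateral cases as failures.

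**Conclusion.** The point holds and should be fixed. On its literal terms, the safety set drops men exposed to the invasive procedure but not to microspheres, and no section says otherwise. The omission can only make the tables miss harms in those men.

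The likely size is modest: about 0.8% to 18% for at least one omitted injury. This rests on 20 procedures started, assumed abandonment and injury rates of 2% to 10% each, and independence between them; screening argues against the upper end. If it does happen, a table can show no injuries where one occurred, although the intervals overlap heavily. The consequence falls mainly on the safety tables, and possibly on later adverse-event follow-up and, through relabelling as screen failure, on the listings. The efficacy analysis is not affected.

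**What to change.** - **9.3.3:** define the Safety Population as all patients in whom the invasive part of the procedure was started, marked by a named step such as arterial access, whether or not microspheres were delivered. Delete the sentence equating it with the ITT set. Starting at any step of Appendix C would be too wide, since its first item is prophylactic antibiotics.
- **9.1:** state that such a patient is not a screen failure and is included in the listings.
- **7.2 and 9.6.1:** state that the date of treatment is the date the procedure was started, so that adverse-event capture and the 12-month period apply to him.
- **9.6:** report the number of procedures with no, unilateral and bilateral embolisation. At present only 9.5.1 separates unilateral from bilateral, and only for IPSS.
- **9.4:** summarise baseline characteristics for the new Safety Population.

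The efficacy set stays as it is. The cost is a few sentences, different denominators for safety and efficacy, safety figures that may look slightly less favourable, and adverse-event follow-up for a few more men (an expected 0.4 to 2 of 20 under the assumed rates).
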